## 3.1.3 Central Imaging Review (MedQIA)

Imaging will be conducted throughout the duration of the study as standard clinical care for HCC surveillance (recurrence or metastasis) and will be no cost to the study. All standard of care imaging scans (MRIs, CTs, or ultrasounds) will be sent to the central imaging core laboratory (MedQIA) and reviewed per the *Imaging Charter*. Assessment of eligibility and HCC recurrence will be made by an independent team of reviewers outside of the patient's care team, coordinated by our imaging core laboratory (MedQIA), per the *Imaging Charter*. Image procedures, acquisition, and transfer guidelines will be harmonized across the clinical sites by MedQIA and the study team. MedQIA uses proprietary computer-aided technologies for image analysis to maximize accuracy and reproducibility and reduce adjudication rates. Tumor measurements will be computed from radiologist-approved volumetric contours, providing data on diameter, volume, density, and heterogeneity. MedQIA was chosen for this study given their past performance, including serving as the imaging core for oncology clinical trial submissions to the FDA with imaging as the primary endpoint.

## 4.0 ELIGIBILITY CRITERIA

## 4.1 Inclusion Criteria

- **4.1.1** Age ≥ 18 years
- **4.1.2** Confirmed diagnosis of liver cirrhosis (Child-Pugh A or B) assessed by the presence of clinical signs, symptoms, body imaging, or liver biopsy
- **4.1.3** Diagnosis of HCC falling within one of the following criteria prior to LRT.

- **a.** One lesion  $\leq$  5 cm or two to three lesions, each  $\leq$  3 cm.
- **b.** One lesion > 5 cm and  $\leq$  8 cm.
- **c.** Two or three lesions, of which at least one is > 3 cm and all are  $\leq$  5 cm each. The sum of all diameters must be  $\leq$  8 cm.
- **d.** Four or five lesions, each < 3 cm. The sum of all diameters must be  $\leq$  8 cm.

#### Criteria fulfillment will be confirmed by the *Imaging Charter* and MedQIA.

- **4.1.4** Initiation of LRT (according to clinical judgement) within 24 months prior to Screening Visit, with adequate response as determined by *Imaging Charter* and MedQIA.
- **4.1.5** ECOG performance status  $\leq$  1 (or Karnofsky  $\geq$  70%; see Appendix A)
- **4.1.6** AST (SGOT) & ALT (SGPT) ≤ 5x institutional ULN
- **4.1.7** AFP < 400 ng/mL
- **4.1.8** Ability to understand and the willingness to sign a written informed consent document and medical release
- **4.1.9** Agree to use adequate contraception (hormonal or barrier method of birth control; abstinence) prior to study entry and for the duration of study participation; for women who are able to become pregnant.
- **4.1.10** Willing and able to comply with trial protocol and follow-up

## 4.2 Exclusion Criteria

- **4.2.1** Current use of statin medication or statin use within 12 months of Screening visit.
- **4.2.2** Current systemic use of medications known to interact with statins and potentially increase toxicity, including (e.g., gemfibrozil, cyclosporine, clarithromycin, colchicine, niacin and fibrates).
- **4.2.3** History of adverse effects, intolerance, or allergic reactions attributed to compounds of similar chemical or biologic composition to pravastatin (i.e., other statin medications)
- 4.2.4 Current use of any other investigational agents
- **4.2.5** Women who are pregnant. Women who are able to become pregnant must have a confirmed negative pregnancy test prior to enrollment.
- **4.2.6** Women who are breastfeeding. It is not known whether pravastatin is excreted into human milk; however, a small amount of another drug in this class does pass into breast milk. Because there is an unknown but potential risk for adverse

events in nursing infants secondary to treatment of the mother with pravastatin, breastfeeding should be discontinued if the mother is treated with pravastatin.

- **4.2.7** Prior liver transplant
- **4.2.8** MELD score ≥ 30.
- **4.2.9** History of chronic myopathy
- **4.2.10** Active malignancy within the past 5 years (excluding HCC, basal/squamous cell skin cancer, or prostate cancer with a Gleason score 6 or less)
- 4.2.11 Known HIV infection
- 4.2.12 Hemophilia
- **4.2.13** Concurrent illness which in the opinion of the investigators would compromise either the patient or the integrity of the data
- **4.2.14** Concurrent excessive alcohol consumption (average alcohol consumption of more than 5 drinks per day)

## 4.3 Inclusion of Women and Minorities

Both men and women and members of all races and ethnicity groups are eligible for this trial.

## 4.4 Source Population

Participants will be recruited from all eligible patients who have liver cirrhosis and a first HCC meeting Milan criteria or OPTN tumor downstaging criteria (described in eligibility). We will recruit patients from liver transplant hepatology clinics and will target patients who are currently waitlisted, or under evaluation, for a liver transplant. Patients who are inactive on the waitlist, or ineligible for a transplant (for reason other than HCC) may still be recruited if they meet all eligibility criteria.

#### 4.5 Recruitment and Feasibility

Recruitment will occur over 3 years. We will identify patients via the physician's upcoming appointments and reviewing their medical records for eligibility. The research staff will notify the study physician that a patient is potentially eligible for the trial based on the prescreen evaluation. The physician will review the eligibility information and notify research staff whether the patient may be considered for participation. A study information packet may be mailed to potential participants. Clinical research staff will call all potentially eligible patients before their scheduled standard of care clinical appointment to introduce the study and answer questions. Patients will be encouraged to review the consent documents with family, friends, and/or other physicians. The patient will be told that the decision to join or not join the study will not affect the medical treatment that s/he receives, and that s/he can withdraw from the study at any time. Patients who wish to participate will be consented into the trial by a study physician.

For potentially eligible patients who may not be mailed a recruitment packet in advance of the regular clinic visit (e.g., new patients who do not already have an established relationship with the physician or patients added to the clinical schedule late), a study physician will introduce the study to the patient during the standard of care clinic visit. The patient will be given a study information packet to take home for review. Clinical research staff will be present at the clinic during this visit and will be available to review the materials in the information packet with the patient and answer questions about the

study. Clinical research staff will follow-up with a phone call to the patient a few days later to evaluate interest in study participation and answer additional questions. Interested patients will be scheduled to come to the clinic to sign informed consent documents with the study physician. Patients who have had all their questions about the study answered on the day they first learn about the study, and who wish to participate, may be consented the same day they are first informed of the research. Patients who do not speak English may be consented according to the policies at their local institutions. In an effort to minimize participant burden and increase the likelihood of enrollment and followup, we will coordinate study visits with usual care appointments and tests to the extent practical.

There will be six study visits. Study Visit 1 (baseline measurements and initiation of the intervention) will occur 0-30 days after the Screening eligibility visit. Follow-up visits will be scheduled at 1 month ( $\pm$  15 days), 3 months ( $\pm$  15 days), 6 months ( $\pm$  15 days), 9 months ( $\pm$  15 days), and 12 months ( $\pm$  15 days) after initiation of the intervention to avoid protocol deviations. Participants will receive \$75 when they complete Study Visits 1, 2, 3, and 5 (which do not coincide with usual care visits or require significant time/burden in addition to the usual care visit) and \$25 when they complete Screening, Study Visits 4 and 6 for their time, transportation, parking, and other expenses related to the study. Participants who complete the entire study will receive \$375.

## Compensation schedule

Screening Visit	Study Visit 1	Study Visit 2	Study Visit 3	Study Visit 4	Study Visit 5	Study Visit 6
\$25	\$75	\$75	\$75	\$25	\$75	\$25

The participant will be contacted prior to the scheduled study visit to confirm or reschedule his/her visit, for example a telephone call 5-7 days prior to the scheduled study visit. If a study participant misses his/her study visit, s/he will be called promptly to reschedule. Study visits will be rescheduled for up to 2 months, at which point the participant is considered lost to follow-up.

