## • Primary Efficacy Endpoint

Following the American Association for the Study of Liver Diseases-Journal of the National Cancer Institute guidelines for trial design in HCC, we have set our primary endpoint as TTR, according to the recommendation for Phase II studies that assess adjuvant therapies secondary to liver directed therapy (33). TTR will be defined as the time from randomization to the first occurrence of a documented HCC recurrence or HCC death, within the 12-month intervention and assessment period. Participants who experience death attributed to their underlying liver cirrhosis, or other cause, will be censored at death date. For participants who do not recur or die and are lost to follow-up prior to the 12-month study visit, analysis of TTR will be censored at their last date of evaluable scan before drop-out.

In this study, we will rely heavily on the mRECIST outcome guidelines and the Liver Imaging Reporting and Data System (LI-RADS) diagnostic algorithm for defining hepatic recurrence (34, 35), and central expert independent radiographic review by MedQIA.

Pathological Definition: Participants who receive a transplant will become ineligible at the time of transplantation. Recurrent HCCs may also be identified at time of transplantation during the examination of the explant by a pathologist. These "incidental" HCCs represent a sizable proportion, amounting to 22% of HCCs among those receiving a liver transplant. Thus, if transplantation occurs and a pathologically confirmed HCC is detected, we will examine these pathologically defined tumors as a **secondary** definition of recurrence.

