## 6.6 Off Agent Criteria

Participants may stop taking study agent for the following reasons:

- Completed the protocol-prescribed intervention
- Adverse event or serious adverse event
- Inadequate agent supply
- Noncompliance/refusal due to non-medical reasons
- Concomitant medications
- Medical contraindication
- Receive a liver transplant prior to completion of the intervention

Participants will continue to be followed, if possible, for safety reasons and in order to collect endpoint data according to the schedule of events. As described in section 6.3, clinical research staff will follow participants by telephone on days  $30 \pm 7$ ,  $60 \pm 7$ , and  $90 \pm 7$  after the participant discontinues the study agent to assess symptoms and adverse events. Standard of care data (medical history, laboratory test results, concomitant medications, HCC surveillance data) will continue to be collected via review of the participant's electronic medical record at the time points specified in the Schedule of Time and Events.

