## 6.7 Removal of Subjects from Study

Patients can be taken off the study treatment and/or study at any time at their own request, or they may be withdrawn at the discretion of the investigator for safety, behavioral or administrative reasons. The reason(s) for discontinuation will be documented and may include:

- Patient voluntarily withdraws (follow-up permitted);
- Patient withdraws consent (termination of treatment and follow-up);
- Patient is unable to comply with protocol requirements;
- Patient demonstrates recurrence of HCC (unless continued treatment with study drug is deemed appropriate at the discretion of the investigator);
- Patient experiences toxicity that makes continuation in the protocol unsafe;

- Treating physician judges continuation on the study would not be in the patient's best interest;
- Patient becomes pregnant (pregnancy to be reported along same timelines as a serious adverse event);
- Development of second primary malignancy (basal/squamous cell skin cancer, or prostate cancer with a Gleason score 6 or less) that requires treatment, which would interfere with this study;
- Lost to follow-up. If a research subject cannot be located to document survival after a period of 2 years, the subject may be considered "lost to follow-up." All attempts to contact the subject during the two years must be documented and approved by the Data Monitoring Committee.

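### Loss to follow-up has two unreconciled definitions (2 months in 4.5, 2 years in 6.7), and the TTR censoring rule in 2.3 neither says which applies nor dates drop-out

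*Combined protocol and SAP*

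**What the plan says.** Two sections define loss to follow-up, and neither refers to the other.

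- Section 4.5, under the compensation schedule, ties it to attendance: "Study visits will be rescheduled for up to 2 months, at which point the participant is considered lost to follow-up".
- Section 6.7, in the list of reasons for removal, ties it to vital status: "If a research subject cannot be located to document survival after a period of 2 years, the subject may be considered" lost to follow-up.

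Section 2.3 (Primary Efficacy Endpoint) makes that status a trigger for censoring. TTR runs to the first documented recurrence or HCC death "within the 12-month intervention and assessment period". "For participants who do not recur or die and are lost to follow-up prior to the 12-month study visit", the rule is that "analysis of TTR will be censored at their last date of evaluable scan before drop-out". The section defines neither loss to follow-up nor drop-out. Section 9.3.1 describes right censoring at the end of the study and competing risks, but gives no rule for participants who are lost.

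Two other sections bear on whether later scans are obtained. Section 3.1.3 says "All standard of care imaging scans (MRIs, CTs, or ultrasounds) will be sent to the central imaging core laboratory (MedQIA") for independent reading. Section 6.6, on stopping the study agent, says "Participants will continue to be followed, if possible, for safety reasons and in order to collect endpoint data according to the schedule of events", and it continues the collection of HCC surveillance data from the electronic medical record.

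**The concern.** The endpoint comes from standard-of-care imaging, which can continue when research visits stop. A rule based on attendance can therefore label someone lost while scans are still being taken at the same hospital.

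Take a participant who misses Visit 3, has not been seen by month 5, and has a routine MRI at month 6 that shows recurrence. By the 4.5 rule this person was lost at month 5; by the 6.7 rule they are not lost. Whether the month-6 recurrence counts depends on which definition is applied and on how drop-out is dated. The study schema first lists surveillance imaging at Visit 3, so the last scan before drop-out could even precede randomization, and 2.3 has no rule for that.

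At stake is whether five sites and the analyst would classify the same participant in the same way on the primary endpoint. If people who miss visits are also more likely to be progressing, censoring them at their last earlier scan would be informative. The documents give no missed-visit rate or pattern, so this is a plausible risk and not a demonstrated one.

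**Working it through.** **Which definition can operate.** The TTR window is 12 months. A 2-year period without contact cannot be completed before the 12-month visit. A visit missed at month 1, 3, 6 or 9 reaches the 2-month limit at month 3, 5, 8 or 11. Of the two written definitions, only the one in 4.5 can trigger the censoring in 2.3. This is an inference: the documents state no link.

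**Two readings of a recurrence after the 2-month point.**

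- *Event:* the 2.3 definition counts a documented recurrence within 12 months, and the censoring sentence covers only people who do not recur.
- *Excluded:* the censoring sentence looks only at scans before drop-out, and under 4.5 drop-out has already happened.

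**The plan's own power figure.** Section 9.3.1 states 80% power with 47 per group, hazard ratio 0.45, two-sided alpha 0.1, 12-month cumulative incidences of 35% (control recurrence) and 20% (competing events), 42 months' accrual, 15 months' follow-up and 10% drop-out.

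- Total control hazard: −ln(1 − 0.55)/12. Split in proportion 0.35 : 0.20, this gives 0.0423 (recurrence) and 0.0242 (competing) per month. Treated recurrence hazard: 0.45 × 0.0423 = 0.0191.
- With drop-out hazard −ln(0.9)/12 and follow-up spread evenly from 15 to 57 months, expected events are 23.8 + 14.0 = 37.8.
- Schoenfeld power is Φ(√E × |ln 0.45|/2 − 1.645) = 0.791 at E = 37.8. The stated 80% is reproduced and is not disputed here.

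**Size of the ambiguity if the excluding reading is always taken.** Assumptions, not document figures: all 65 per arm are analyzed; TTR stops at 12 months; 35% and 20% are net risks; the missed visit is equally likely to be at month 1, 3, 6 or 9; every later recurrence would have been seen on a routine scan and is dropped.

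1. Hazards per month: λ₀ = −ln(0.65)/12 = 0.0359; λ₁ = 0.45 × λ₀ = 0.0162; competing c = −ln(0.80)/12 = 0.0186.
2. Cumulative incidence: F(t) = λ/(λ + c) × (1 − e^−(λ+c)t). F(12) = 0.3162 for control and 0.1585 for pravastatin.
3. Expected events: 65 × (0.3162 + 0.1585) = 30.9.
4. F(12) − F(s) at s = 3, 5, 8, 11. Control: 0.2169, 0.1591, 0.0834, 0.0192, mean 0.1196. Pravastatin: 0.1125, 0.0844, 0.0457, 0.0108, mean 0.0633.
5. Events dropped at loss fraction d: 65 × d × (0.1196 + 0.0633). At d = 0.10 this is 6.5 × 0.183 = 1.19.
6. Power: √30.86 × 0.7985/2 − 1.645 = 0.573, so Φ = 0.717. With 30.86 − 1.19 = 29.67 events, the argument is 0.530 and Φ = 0.702.

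| Loss fraction | Events dropped of 30.9 | Power |
|---|---|---|
| none | 0 | 0.717 |
| 5% | 0.6 | 0.709 |
| 10% (the plan's drop-out) | 1.2 | 0.702 |
| 15% | 1.8 | 0.694 |
| 28% (the plan's full shrinkage from 130 to 94) | 3.3 | 0.674 |

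The 0.717 is a base for measuring the difference on a 12-month window. It should not be compared with the plan's 80%, which rests on longer follow-up.

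**Higher-risk non-attenders.** If the recurrence hazard is doubled in the lost participants only (2λ in steps 2 and 4), the two arm means sum to 0.290. At 10% loss, 6.5 × 0.290 = 1.9 events.

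**The case against.** The strongest defense is that the plain text already gives the right answer. The censoring sentence in 2.3 is limited to people who do not recur, so a participant with a documented recurrence at month 6 is an event. A scan taken during the 2 months of rescheduling precedes drop-out and counts on any reading. Routine scans go to central review under 3.1.3, and 6.6 keeps collecting surveillance data from the record. The two definitions also serve partly different ends: visit scheduling in 4.5, and tracing of survival in 6.7.

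Much of this stands, and it rules out two stronger readings that a reader might infer.

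- *That recurrences after a missed visit are discarded.* No section says so. Exclusion is one possible reading of an undated term.
- *That the 2-month rule ends data collection, because loss to follow-up is a reason for removal in 6.7.* That item carries its own 2-year definition, so a visit 2 months late does not meet it. Section 6.7 attaches an end to follow-up only to withdrawal of consent.

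What the defense does not settle is the gap itself. Section 6.6 is written for participants who stop the agent and does not name those who stop attending. The footnote to the schedule of events ties image review to study visits 3 to 6. Section 5.10 sends removed patients to the follow-up in 6.3, which is telephone calls on symptoms and adverse events. And a later scan, even once collected, still meets the undated drop-out in 2.3.

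**Conclusion.** The point holds as an internal inconsistency on the primary endpoint. Two definitions conflict, the TTR rule picks neither, and the same later recurrence can be an event or excluded. The mismatch is certain from the text; its consequence for any participant is an ambiguity.

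The likely effect is small: about 1 event in roughly 31 and 1.5 points of power at 10% loss. That rests on average risk among those lost, losses spread evenly over the visits, and every later recurrence being excluded. It is nearer 2 events if non-attenders have twice the recurrence hazard. The reason to act is that the censoring date should be fixed in advance and be the same at every site; lost power is a minor part of it. This is a minor correction.

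**What to change.** - **4.5:** call a visit more than 2 months late a missed visit, not loss to follow-up.
- **2.3:** state that any recurrence on a centrally read scan within the 12-month window counts, whatever the visit attendance. Otherwise censor at the last evaluable scan actually obtained in that window, and say which date applies if there is none after randomization. Define a participant as lost for TTR only on withdrawal of consent for follow-up, or when no further scan or record contact can be obtained.
- **6.6:** extend the chart collection of HCC surveillance data expressly to participants who stop attending visits.
- **6.7:** limit the 2-year definition to survival tracing.

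In the same edit, check the statistical methodology entry in the Study Summary. It confines the primary analysis to those who complete the 12-month imaging and blood collection, which would leave lost participants out and does not fit with censoring them.

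The cost is the wording and a little more record review by existing coordinators, with no added visits or scans. It should be settled before database lock and unblinded analysis; after that, the choice would be post hoc.

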# 4.6 Pre-Screen Medical Chart Review - Initial determination of eligibility and recruitment

Patients who were identified as a potential participant will be pre-screened for eligibility based on the most updated information in their medical charts, prior to their visit. The medical records will be reviewed by the clinical research staff to determine initial eligibility as specified in the inclusion and exclusion criteria. Medical charts will be reviewed for age, cirrhosis diagnosis, HCC diagnosis, HCC treatment history, prior liver transplant, prior statin use, prohibited concomitant medications, previous malignancies, medical contraindications, laboratory results, and HCC characteristics (size and number of tumors).

## 4.7 Consent and Eligibility

The study physician will review the consent document with the patient and will answer any questions regarding the trial. After the patient's questions have been answered, the study physician will obtain signatures on the consent documents from patients who wish to volunteer for the study. The patient will review and sign the study consent form and HIPAA authorization. Copies of each document will be given to patients who agree and consent into the study, the original signed consent will be placed in the research binder, and copies will be distributed/maintained per local institutional policy. Written consent will be obtained before any research related procedures are initiated. After consent has been obtained, the screening visit and procedures will be completed. Final determination of eligibility will be conducted using an eligibility checklist that requires double signoff (by the study physician and study team member) and also central eligibility verification by the Quality management core (QMC) at Cedars-Sinai.

